
The following documents are currently attached to this item:

There are no documents attached for this item.

Deception

Does your project use deception? Deception could be considered any direct misinformation presented to the subject or omission of key information pertaining to the design or nature of the project.

No

International Research

Are you conducting research outside of the United States?

No

Analysis Plan

Hypotheses 1. We hypothesize that over the 24-week study period, compared to usual care, the hybrid intervention will lead to a higher rate of adherence to daily glucose self-monitoring. 2. Our secondary hypothesis is that compared to DFI alone, the hybrid intervention will lead to a higher rate of adherence to daily glucose self-monitoring. 3. Our exploratory hypotheses are that compared to usual care and DFI alone, the hybrid intervention will lead greater improvements in glycosylated hemoglobin. Outcome measures The primary and secondary outcome measures will be adherence rate (constructed by summing the number of days in the study period that the glucometer was used divided by the total number of days in study period). The exploratory outcome measure will be change in glycosylated hemoglobin from baseline to 24 weeks follow-up assessment. Statistical analyses We will test our hypotheses with an intent-to-treat analysis using a modified Poisson regression model to obtain relative

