risk of low adherence and a linear regression model to obtain the between-arm difference in change in glycosylated hemoglobin. We will adjust these models for any unbalanced baseline covariates to increase efficiency. For exploratory purposes, we will do a per protocol analysis focusing on the subgroup of patients in the hybrid intervention who actually received CHW support, as compared to the patients in the DHI alone arm who would have received support based on low adherence or elevated glucoses. We will also explore predictors of adherence and glycosylated hemoglobin across all three arms. Sample size calculations Based on a similar 24-week trial, we assume that the adherence rate in the usual care arm will be 40% and the rate in the hybrid intervention will be 80%. In the prior trial, the adherence rate in the usual care arm was 47%; however this trial had a lower risk population (higher income and lower baseline glycosylated hemoglobin), and a longer financial incentive period. In this same trial, the adherence rate for the DFI alone arm was 70%; therefore the estimate of 80% adherence in the hybrid DFI/CHW arm seems reasonable. Using a two-sample comparison of proportions (usual care versus hybrid), we will require a sample size of 28 patients per arm to detect these differences with 80% power, assuming a Type I error rate of 0.05. Given the vulnerability and transience of this patient population, it is important to account for loss to follow-up, which we assume based on prior trials to be 20%. Therefore, we estimate that we will have to enroll 34 patients in each arm to end up with our minimal sample size. Our planned enrollment of 50 patients in each arm will easily allow us to meet this threshold. Our planned sample size will also allow us to detect a difference between DFI alone and hybrid arms (the secondary outcome), assuming the DFI arm has an adherence rate of 48% and the hybrid arm has a rate of 80%. In reality, we might see higher adherence than 48% in the DFI alone arm based on a prior similar trial as above in which the DFI arm had a 70% adherence. However, it is possible in this trial focusing on a vulnerable population, DFI alone may result in lower adherence. Missing data Efforts will be made to collect complete information on patients including 3 attempts to contact each patient via telephone and the provision of honoraria for completion of follow-up. We will check the medical record of those lost to follow-up and extract from the electronic medical record any relevant glycosylated hemoglobin that occurred within 4 weeks of the study completion date. We will track all missing values and assess the pattern of missing data and whether the missingness is non-ignorable. If appropriate, we will consider statistical methods such as multiple imputation.

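### The primary outcome is a share of days with glucometer use, but the only adherence model estimates a relative risk of low adherence, for which no cut-off is given

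*Combined protocol and SAP*

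**What the plan says.** Primary outcome variable(s) and Analysis Plan, Outcome measures, give the same definition: "The primary and secondary outcome measures will be adherence rate (constructed by summing the number of days in the study period" on which the glucometer was used, over all days in the study period. This is one number between 0 and 1 per participant. Hypotheses 1 and 2 are worded on that scale. Over 24 weeks, compared with usual care (primary) and with DFI alone (secondary, as the Analysis Plan uses the word), "the hybrid intervention will lead to a higher rate of adherence to daily glucose self-monitoring".

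Statistical analyses names one model for adherence, "using a modified Poisson regression model to obtain relative" "risk of low adherence and a linear regression model", the latter being for glycosylated hemoglobin.

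Sample size calculations states that "we assume that the adherence rate in the usual care arm will be 40% and the rate in the hybrid intervention will be 80" per cent. It continues: "Using a two-sample comparison of proportions (usual care versus hybrid), we will require a sample size of 28 patients per arm". The secondary contrast is sized "assuming the DFI arm has an adherence rate of 48% and the hybrid arm has a rate of 80" per cent.

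The phrase low adherence is given content only in the rule for assigning community health worker (CHW) support (Design; Procedures, Step Seven). That rule looks at any 2-week period in the first 12 weeks and is combined with glucose readings.

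**The concern.** The outcome and hypotheses concern a mean share of days. The model concerns the risk of an event. To get from one to the other, someone must decide what share of days over 24 weeks counts as low, and the plan does not say. The unit is not stated for the model either, though the sample size counts patients.

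Two things are at stake. First, two competent statisticians following this plan could report different effect measures of different size, neither of them the difference in adherence rate that the hypotheses describe. Second, if the cut-off is settled after the data are seen, the 5% error rate no longer holds, and the result for hybrid versus DFI alone may depend on which cut-off was chosen.

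**Working it through.** **1. The plan's own figure.** Two-sided comparison of proportions, alpha 0.05, power 80%, p1 = 0.40, p2 = 0.80, mean 0.60:

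n = [1.96·√(2·0.60·0.40) + 0.842·√(0.24 + 0.16)]² / 0.40² = 22.3 per arm.

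With continuity correction: (22.3/4)·[1 + √(1 + 4/(22.3·0.40))]² = 27.1, so 28. The stated figure reproduces. For 0.48 v 0.80 the same steps give 34.1, then 40.1, so 41, close to the 40 per arm left after the stated 20% loss (50 × 0.8). The sample size thus treats 40%, 48% and 80% as proportions of patients with a yes/no result, although the text calls them adherence rates.

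**2. Is 28 too small for the outcome as defined?** No. The largest possible pooled SD for shares with means 0.40 and 0.80 is √[(0.24 + 0.16)/2] = 0.447. A comparison of means then needs 2·(2.802·0.447/0.40)² = 19.6 per arm.

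**3. Does the CHW trigger supply the cut-off?** No. It applies to 2-week windows in the first 12 weeks, can be met through glucose values alone, and is used to assign support. The Analysis Plan draws on it only for the exploratory per-protocol subgroup.

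**4. How much does the cut-off matter?** The documents give no SD and no cut-off, so these are assumptions: adherence follows a beta distribution with SD 0.25–0.35, over 168 days, with 40 evaluable per arm. The beta parameters are m·k and (1 − m)·k, with k = m(1 − m)/SD² − 1.

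Relative risk of low adherence, hybrid v usual care, at SD 0.25:
- cut-off 30%: 0.069/0.403 = 0.17
- cut-off 50%: 0.147/0.653 = 0.23
- cut-off 90%: 0.469/0.977 = 0.48

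The ratio of mean non-adherence is 0.20/0.60 = 0.33. The same data can therefore give quite different headline figures.

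Simulated power (per-patient log relative risk Wald test; Welch test for means):

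| Event | 40% v 80% (primary) | 48% v 80% (secondary) |
|---|---|---|
| cut-off 30% | about 88% or more | about 59–65% |
| cut-off 40% | about 95% or more | about 76–87% |
| cut-off 50% and above | about 98% or more | about 87% or more |
| means | over 99% | about 97% or more |

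**5. False positives with no true difference** (both arms at 40, 48, 60 or 80%):
- one cut-off fixed in advance: 1–5%
- any of 50, 70, 80 or 90% reported if significant: about 7–14% two-sided
- the same, counting only results that favour hybrid: about 4–7%, against a nominal 2.5%
- comparison of means: about 5%

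**The case against.** The best defence is that the gap is narrow. The 24-week window is stated in hypothesis 1, and the rate is taken over the study period. The sample-size text counts patients, so the natural reading is one yes/no per patient, and only one number is missing. All of that stands.

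A reader might go further and infer that the analysis has no time window, that the sample size rests on yet another variable, or that days would be analysed as if independent. The documents support none of these. The window is given, the sample size follows the per-patient reading, and nothing in the plan proposes treating days as independent. Modified Poisson uses a robust variance, and applied to each patient's share of missed days it keeps the false-positive rate at about 5%. That version would match the outcome, but the plan does not describe it.

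The 7–14% is also a worst case. It assumes four candidate cut-offs and free choice among them, and nothing in the documents says the cut-off will be chosen that way. Potential Study Risks says arms stay under code letters until analysis is complete. This makes it harder to favour a particular arm, but it does not fix the event, and a cut-off could still be picked because it separates the arms.

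What remains is that, with the unit granted as the patient, the event still cannot be coded from the plan.

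**Conclusion.** The point holds as a mismatch between the primary outcome and its analysis, and should be settled before the data are seen. The stated outcome is a share of days, while the only adherence model needs a yes/no event that the plan does not define.

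A reader might take this as a power failure or an arithmetic error. It is neither. The stated 28 per arm reproduces, and 50 per arm remains adequate for hybrid versus usual care, with power of about 88% or more at any cut-off from 30% to 90%.

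The consequences are an undetermined effect measure, an error rate that could reach about 7–14% if the cut-off is chosen from the data, and a secondary contrast whose power depends on the cut-off (about 59–65% at 30%, 87% or more from 50% upwards). The plan itself says that "In reality, we might see higher adherence than 48% in the DFI alone arm", which would narrow that contrast and make the choice matter more.

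These sizes rest on assumed beta distributions, SD 0.25–0.35 and 40 evaluable per arm. The mismatch itself rests only on the text.

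**What to change.** Before the data are seen:

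- **Preferred.** Make the primary analysis a regression of each participant's 24-week adherence rate on arm (linear with robust standard errors, or fractional/quasi-binomial). Report the difference in mean adherence with 95% CI for hybrid versus usual care, then hybrid versus DFI alone. Keep modified Poisson as supportive, with one fixed per-patient cut-off.
- **If modified Poisson stays primary.** Define the event in one sentence: either a 24-week rate below one stated cut-off per patient, or no glucometer use on a patient-day with robust errors clustered by patient. Word the outcome and hypotheses to match.
- **Either way.** State whether 40%, 48% and 80% are mean rates (with an assumed SD) or shares of patients.

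The cost is one or two sentences of amendment and a clarified sample-size paragraph, with no new patients or data. The downside is that a comparison of means can have less power than a high cut-off when the true difference is smaller than planned. For an illustrative 60% v 80% at SD 0.35, power is about 70% for means against 74–95% at cut-offs of 70–90%. The 60% is the rate that Background reports from another study, not a planning value.

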A trial of a hybrid DFI/CHW intervention that incorporates strategies for coping with failure among a population of low-income patients with diabetes. Diabetes is an ideal condition in which to test this innovative intervention; the challenges of carrying out healthy behaviors for patients with diabetes have been well described. In addition, the enormous public health and economic challenge of diabetes is concentrated among disadvantaged populations: 18% of African Americans and 16% of people without a high school education have diabetes. Finally, diabetes is a condition that is well-suited to the study of self-monitoring, which appears to be a key factor in behavior change: glucose self-monitoring improves

outcomes among insulin-requiring diabetics and glucometers are covered by Medicaid in all states. A diabetes-specific trial can provide valuable insights that can be extrapolated to other diseases. Digital health applications extend to monitoring of weight, medication adherence, physical activity, blood pressure and other conditions. IMPaCT is adaptable and has been tested across many diseases. If we establish the effectiveness of a hybrid DFI/CHW intervention in this population, we will be able to generalize the intervention more broadly to improve health among low-income patients. We will test an innovative hybrid of two of the most promising and synergistic approaches for improving health among low income people in a way that is guided by behavioral and social science. This study will provide new knowledge of the pathways to behavior change and has the potential to improve the health of low-income individuals.

Primary outcome variable(s)

Primary outcome: Adherence rate (constructed by summing the number of days in the study period that the glucometer was used divided by the total number of days in study period.)

Secondary outcome variable(s)

The secondary outcome measure will be change in glycosylated hemoglobin from baseline to 24 weeks follow-up assessment.

Background

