Participants will receive a \$50 pre-paid gift card upon completion of enrollment (baseline survey and laboratory testing) and \$50 upon completion of a 3 month follow up visit for glucometer data extraction and finally \$100 gift card at the 6 month follow-up assessment (baseline survey, laboratory testing, and glucometer data extraction.) Participants who complete a qualitative interview will receive an additional \$20 gift card. We are submitting a piece of paper that we would like to give to participants explaining when they can expect to be paid for the study. We hope this will offer clarity to the process used for uploading money onto ClinCards. We have uploaded a copy of this document below. Due to restrictions on in-person non-essential research visits due to COVID-19, we propose to split 3-and 6-month study compensation into 2 payments. For 3-month study visits, we will look to conduct adverse event screening with patients telephonically, for which they will receive 1 half (\$25) of their 3-month compensation. As soon as is safely possible, we will aim to complete an in-person 3-month visit, to collect biometric data (from patient glucometers). At the completion of this component of the 3-month visit, patients would be provided with the other half (\$25) of their 3-month compensation. Similarly, for 6-month follow-up we will aim to complete adverse event screening and psychometric surveys via telephone, for which subjects will be compensated 1 half (\$50) of the 6-month compensation. Then, as soon as possible, we will look to complete the 6-month biometric data collection for glucometer data and hemoglobin a1c testing. At the completion of these steps, participants would receive the other half (\$50) of the 6-month follow-up compensation. o Due to the COVID-19 pandemic, we have been delayed in completing study follow-up visits. Given that participants are not able to complete follow-up visits as scheduled we have not been able to dispense follow-up compensation to study participants at the anticipated times (approximately 3- and 6- months post-enrollment). In order to honor the financial expectations we set with participants, we propose to attempt to send follow-up payments to participants with whom we are unable to meet due to COVID, regardless of whether they complete any follow-up activities. Specifically, for any patients whose planned follow-up date has already passed, we will aim to provide the full follow-up visit compensation amount via ClinCard as soon as possible. For patients with future planned follow-up visit dates, if the date of their planned follow-up arrives, and we are still unable to meet with them due to COVID, we will aim to issue their full visit compensation via ClinCard

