
the correct phone number using contact verification technology. Step Five: Labs 1. Walk the patient to the laboratory to have their blood drawn for HbA1c evaluation. 2. Provide the patient with a gift card and half page sheet with payment information Step Six: How to Use the Glucometer 1. Provide the patient with a glucometer if they don't already have one. 2. Review the user guide with the patient and answer any questions they may have about using their glucometer. 3. Reinforce/explain to the patient not to delete their glucose reading log from the glucometer because we will extract the log from the glucometer at subsequent visits. Abnormal Blood Glucose Safety Protocol: The study clinician will be notified by the way to health platform if participants glucose is either extremely low or high (60 or 400 mg/dL) and respond accordingly. The study clinician will contact these patients to address the issue. Step Seven: CHW escalation 1. The way to health platform will notify the study team of any individuals who have low adherence (no self-monitoring) or elevated glucose readings (300 mg/dL) for 30% of days over any 2 week period in the first 12 weeks of the study. These individuals will be assigned to receive ongoing CHW support for the duration of the 24-week study period 2. The study team should notify the CHW and send them the patients redcap ID. The CHW will follow up with the patient in 1-2 days. Step Eight: 3 Month Follow Up 1. One month prior, contact the patient to set a date/time for their 3 month follow up appointment. (If patients are unable to be reached, then we will send a letter to their home requesting that they contact us to set up a follow-up appointment.) 2. At the appointment, obtain the blood glucose log of readings from the patients glucometer. 3. Provide the patient with a gift card. Follow up visit is concluded. 4. The window to complete all 3-month follow-up procedures may be extended in cases where patients were prevented from completing visits within the original window due to COVID-19 restrictions. Step Nine: 6 Month Follow Up and Labs 1. One month prior, contact the patient to set a date/time for their 6 month follow up appointment. (If patients are unable to be reached, then we will send a letter to their home requesting that they contact us to set up a follow-up appointment.) 2. At the appointment, obtain the blood glucose log of readings from the patients glucometer. 3. Administer the follow up redcap survey 4. Walk the patient to the laboratory to have their blood drawn for HbA1c evaluation. 5. Provide the patient with a gift card. Follow up visit is concluded. 6. The window to complete all 6-month follow-up procedures may be extended in cases where patients were prevented from completing visits within the original window due to COVID-19 restrictions. Any Engage Study patients screened for recruitment into routine care community health worker programs at Penn Medicine will have their enrollment deferred until their study participation is complete. We will track all screened patients that are deferred because of Engage Study participation and contact them afterwards to offer enrollment into our routine care community health worker program. You may also be contacted during this study as a part of our quality review. If this happens you will just be asked a few questions about how the study has been going and your experiences with the steps listed above.

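### Baseline HbA1c is sure of a place in the HbA1c change model only if judged unbalanced; always including it costs one degree of freedom and can gain precision

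*Combined protocol and SAP*

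**What the plan says.** Under Analysis Plan, Statistical analyses, the HbA1c analysis is "a linear regression model to obtain the between-arm difference in change in glycosylated hemoglobin". The only rule on covariates follows it and covers both this model and the adherence model: "We will adjust these models for any unbalanced baseline covariates to increase efficiency". No covariate list is given, imbalance is not defined, and baseline HbA1c is not named as a fixed term anywhere. The planned search for predictors across the three arms is a separate exploratory analysis and does not put baseline HbA1c in the between-arm model.

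The hypothesis at stake is that "compared to usual care and DFI alone, the hybrid intervention will lead greater improvements in glycosylated hemoglobin". The Analysis Plan ranks this outcome as exploratory ("The exploratory outcome measure will be change in glycosylated hemoglobin from baseline to 24 weeks follow-up assessment"), while the section Secondary outcome variable(s) ranks it as secondary ("The secondary outcome measure will be change in glycosylated hemoglobin from baseline to 24 weeks follow-up assessment").

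The covariate will be in hand. Step Five of Procedures, at enrolment, reads "Walk the patient to the laboratory to have their blood drawn for HbA1c evaluation", and Subject compensation ties the enrolment payment to laboratory testing.

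**The concern.** The rule's stated purpose is efficiency, but its trigger is imbalance, and these are different things. A covariate sharpens a treatment comparison to the extent that it explains outcome variation, whether or not the arms happen to differ on it. A change score subtracts baseline with a slope fixed at 1. Analysis of covariance estimates that slope, and it gains whenever the true slope is not 1, including when the arms are perfectly balanced.

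At stake is precision in two comparisons: hybrid against usual care, and hybrid against DFI alone. Each would have about 40 evaluable patients per arm. Because imbalance is undefined, two analysts could also fit different models to the same data. Bias and type I error inflation are not at stake: under randomisation the change-score comparison is valid, and the rule looks only at baseline data.

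**Working it through.** **1. Inputs from the documents.** Planned enrolment is 50 per arm in three arms (Accrual). On attrition, Sample size calculations says "it is important to account for loss to follow-up, which we assume based on prior trials to be 20" per cent. So 50 × (1 − 0.20) = 40 evaluable per arm. The plan states no standard deviation, power or detectable difference for HbA1c, so it has no HbA1c figure to reproduce. Its sample size rests on adherence: 40% against 80%, 80% power, alpha 0.05 (two-sided assumed) gives 23 per arm without and 28 with a continuity correction. The stated 28 reproduces, and nothing below touches it.

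**2. Gain from always adjusting.** Let k be follow-up SD divided by baseline SD, and r the correlation between baseline and follow-up, with baseline variance set to 1.

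- Variance of change: k² + 1 − 2rk
- Residual variance after adjusting for baseline: k²(1 − r²)
- Ratio: k²(1 − r²) / (k² + 1 − 2rk)

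The two variances differ by (1 − rk)², so the ratio never exceeds 1 and equals 1 only when rk = 1. With k = 1 it reduces to (1 + r)/2: 0.65, 0.75, 0.85 and 0.90 at r = 0.3, 0.5, 0.7 and 0.8.

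**3. Cost.** Residual degrees of freedom fall from 78 to 77 with two arms, or from 117 to 116 with three. The critical t moves from 1.9908 to 1.9913, or from 1.9804 to 1.9806. The average variance inflation is 1 + 1/76 = 1.013, or 1 + 1/115 = 1.009.

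**4. Assumed range for k and r.** Patients are selected on a recent HbA1c. The comparison sign is lost in the text of Key inclusion criteria, so a floor of 9% is assumed. Selecting on a high value narrows the baseline spread more than the follow-up spread. That makes k larger than 1 and gives smaller gains than k = 1 would suggest.

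Assume that screening (S), baseline (B) and follow-up (F) values are jointly normal before selection, with mean 7.5 or 8.0 and SD 1.5 or 1.8. Take correlations of 0.40 to 0.90 in steps of 0.05, with S–F no higher than the other two. Let a = (9 − mean)/SD, let L be the normal density at a divided by the upper tail beyond a, and let d = L(L − a). After selection, in units of the original variance:

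- Var(B) = 1 − d·r(SB)²
- Var(F) = 1 − d·r(SF)²
- Cov(B, F) = r(BF) − d·r(SB)·r(SF)

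Example with mean 7.5, SD 1.5 and correlations SB 0.8, BF 0.6, SF 0.5: a = 1, L = 1.525, d = 0.801. Then Var(B) = 0.487, Var(F) = 0.800 and Cov = 0.280, so k = 1.28, r = 0.45 and the ratio is 0.88.

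Over all 1,960 valid grid points the ratio has minimum 0.656, quartiles 0.814, 0.888 and 0.956, and maximum 1.000. It is below 0.76 at 11.4% of points and above 0.95 at 26.9%. A ratio of 0.76 is worth 40/0.76 = 52.6 patients per arm in the unadjusted analysis instead of 40. Grid shares are not probabilities.

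**5. How often the rule would include baseline HbA1c.** With 40 per arm, a standardised difference (SMD) has standard error √(2/40) = 0.224. A cut-off of 0.2 lies 0.89 standard errors out and is exceeded in 37% of two-arm comparisons. A cut-off of 0.1 is exceeded in about 66%. Significance cut-offs of 0.05 and 0.20 give 5% and 20%. If the largest of the three pairwise differences is used, the figures are 65% (above 0.2) and 90% (above 0.1).

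**6. What each reading delivers.** Simulation with two arms of 40, k = 1.2, r = 0.5 and 40,000 runs. The formula gives 1.08/1.24 = 0.871, or 0.882 after the 1.013 inflation; the simulated ratio is 0.879. The effect is set to give 80% power unadjusted.

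| Rule | Baseline enters | Variance ratio | Share of gain | Reported SE² (relative) | Power |
|---|---|---|---|---|---|
| Never | 0% | 1.00 | – | 1.01 | 0.804 |
| p < 0.05 | 4.9% | 0.966 | 28% | 1.00 | 0.808 |
| p < 0.20 | 19.8% | 0.924 | 63% | 0.99 | 0.817 |
| SMD > 0.2 | 37.1% | 0.897 | 85% | 0.97 | 0.825 |
| SMD > 0.1 | 65.7% | 0.881 | 98% | 0.93 | 0.836 |
| Always | 100% | 0.879 | 100% | 0.89 | 0.848 |

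Share of gain is (1 − ratio)/(1 − 0.879). Loose cut-offs keep most of the true variance gain, but less of it reaches the reported standard error and hence the power. Using the largest of the three pairwise differences, power is 0.835 (above 0.2) and 0.844 (above 0.1).

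**7. Where there is little or nothing to gain.** At k = 1.2, r = 0.7, power is 0.808 always adjusted against 0.800 unadjusted. At k = 1.3, r = 0.75, where rk = 0.975, it is 0.797 against 0.802. The worst simulated variance ratio was 1.01 (k = 1.5, r = 0.7).

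**8. Type I error** over six (k, r) combinations: unadjusted change 4.8–5.2%, conditional rules 3.6–5.2%, always adjusted 4.9–5.2%. Nothing is inflated; the conditional rules can be slightly conservative.

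**The case against.** The strongest reply is about weight. The Analysis Plan calls HbA1c exploratory and sets no precision target for it, so no stated goal is missed. The fair comparison is always adjusting against the plan's rule, not against no adjustment. In the tabulated case that is 0.848 against 0.825 or 0.836 for the looser cut-offs, and with three arms 0.848 against 0.835 or 0.844. Only the strict p < 0.05 reading loses about 4 points, and the plan does not specify that reading. The tabulated case also sits near the median gain; elsewhere the gain vanishes. Every size rests on HbA1c values that the documents do not give.

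All of this stands as a limit on size. It does not rescue the rule. The plan commits to no cut-off, so the favourable readings cannot be relied on. None of the rules compared beats always adjusting by more than the roughly 1% cost of one covariate. The outcome is also secondary elsewhere in the same document, and the Abstract puts it in the trial's main hypothesis. It is fair to say that the rule serves its aim incompletely rather than not at all.

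Two further points are correct. Follow-up was already under way, so a change needs a dated record as well as new wording. And imbalance would remain undefined for the adherence model and for other covariates.

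**Conclusion.** The concern holds. As written, the plan guarantees baseline HbA1c a place in the HbA1c model only if it is judged unbalanced, and always including it is the better method for the purpose the plan states. This is an improvement in efficiency only.

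On the assumed grid the gain in variance is typically around 11%, with 89% of grid points between 0 and 24%. The remaining 11%, at lower correlations, reach 34%. The gain is under 5% at 27% of points. Against that, the loss is about 1% at worst. How much the plan's own rule would recover depends on a threshold that it does not state.

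Confidence is high on the reading of the text and the direction of the effect. The magnitude depends on the assumed means, standard deviations, correlations and eligibility floor. The adherence analysis, the sample size and the validity of the HbA1c comparison are unaffected.

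**What to change.** In Statistical analyses, state that the HbA1c model always includes baseline HbA1c as a covariate (analysis of covariance), whatever the observed balance, and that observed imbalance does not decide whether it is included.

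The cost is one sentence and one degree of freedom. No new data are needed, because the enrolment blood draw already supplies the value. Date and record the change before the arms are decoded; Potential Study Risks says that they carry code letters until the analysis is agreed to be complete.
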